1. PROTOCOL SUMMARY

1.1. Synopsis

Protocol Title

A Phase 1 Placebo-controlled Study of the Safety and Tolerability of Rectally Administered, Multiple-ascending Doses of IW-3300 in Healthy Subjects

Short Title

A Phase 1 Study of Multiple-ascending Doses of IW-3300 in Healthy Subjects

Rationale

The aim of this study is to assess the effects of IW-3300 administered rectally, once-daily for 7 days in healthy subjects. IW-3300 is a novel, 13-amino-acid, guanylate cyclase C (GC-C) agonist peptide. GC-C, the target of IW-3300, is predominantly expressed on the luminal surface of the small and large intestines. Preclinical models provide preliminary evidence which suggests that when GC-C receptors are stimulated, intracellular cyclic guanosine monophosphate (cGMP) is secreted across the basolateral membrane of colonic epithelial cells in the submucosa by multidrug resistance proteins MRP4 and MRP5. This decreases the activity of afferent nerve fibers located in the colonic wall, resulting in reduced visceral pain, which ultimately produces an analgesic effect in other organs of the abdominopelvic region via action mediated through the common afferent pathways.^(1, 2) Because of these analgesic effects, IW-3300 is being developed as a rectally-administered therapeutic for the treatment of interstitial cystitis/bladder pain syndrome (IC/BPS), a chronic and debilitating condition for which there are no safe, effective treatment options. Data from this current study will be used to enable a Phase 2 safety, tolerability, and efficacy study of IW-3300 in subjects with IC/BPS. More information on the pharmacology and safety of IW-3300 is provided in Section 2.

Objectives and Endpoints

Objective	Endpoints
Primary	
To assess the safety and tolerability of 7-day dosing with multiple-ascending doses of IW-3300 administered rectally via enema in healthy subjects	Incidence of treatment-emergent adverse events (TEAEs) Incidence of treatment-emergent serious adverse events (TESAEs)
Exploratory	
To summarize the pharmacokinetics (PK) of 7-day dosing with IW-3300 administered rectally via enema in healthy subjects	PK parameters (IW-3300 and metabolites in plasma)
To explore potential changes to the microbiome with 7-day dosing with IW-3300 administered rectally via enema in healthy subjects	Change in 16s RNA based analysis of gut microbiome composition at the genus level from baseline to 7 days post IW-3300 administration

Overall Design

This is a Phase 1, single-center, randomized, double-blind, placebo-controlled, multiple-ascending-dose study of IW-3300 administered rectally as a low-volume enema in healthy adult subjects. This study will assess the effect of IW-3300 on safety, tolerability, and PK, and also explore the potential effect of IW-3300 on gut microbiome composition.

Subjects in each cohort will progress through 3 study periods: (1) Screening Period, (2) Clinic Period, and (3) Follow-up Period; these periods and the progression between cohorts are illustrated in the study schematic ([Figure 1](#)).

A Dose Escalation Committee will conduct blinded reviews of all the safety/tolerability parameters of the IW-3300 100- μ g dosing cohort through Discharge (Day 8) in order to make a decision regarding dose escalation to the next IW-3300 dosing cohort. The Dose Escalation Committee will include sponsor and contract research organization (CRO) representatives.

Disclosure Statement

This is a multiple-ascending-dose safety and tolerability study with 4 possible treatments (placebo, 2 dose levels of IW-3300, and an optional 3rd dose level of IW-3300) that is subject- and investigator-blinded.

Number of Subjects

A total of up to 27 subjects will be randomized in the study (2 cohorts of 9 subjects each, and an optional 3rd cohort of 9 additional subjects). Within each cohort, 6 subjects will be randomized to IW-3300 and 3 subjects will be randomized to placebo.

Intervention Groups and Duration

The study will evaluate multiple-ascending doses of IW-3300 in a double-blind manner. The 9 subjects within each cohort will be randomized to receive IW-3300 (6 subjects) or placebo (3 subjects), administered rectally (as a low-volume [20 mL] enema) following a fast of at least 6 hours (refer to the Schedule of Activities [SoA; [Table 1](#)] for additional details regarding dosing instructions) once daily for 7 days. The planned cohorts are:

- Cohort 1: IW-3300 100 μ g or matching placebo rectal dose once daily
- Cohort 2: IW-3300 300 μ g or matching placebo rectal dose once daily
- Cohort 3 (optional): IW-3300 >100 μ g but <300 μ g or matching placebo rectal dose once daily (decision to enroll this cohort will be determined after safety reviews of previous cohorts, in the case of intolerance at 300 μ g but tolerability at 100 μ g)

Dosing in Cohort 2 and optional Cohort 3 will only proceed following a review of safety data from the previous cohort(s), including adverse events (AEs), clinical laboratory test results, vital signs, and 12-lead ECGs. The determination of dose escalation will be made at a meeting of the Dose Escalation Committee.

Treatment duration will be 7 days; subjects will be followed in the Phase 1 clinical research unit (CRU) for the duration of dosing, until at least 24 hours after the last dose of study drug and

[figure not shown]
contacted by phone for follow-up approximately 2 weeks after the last dose. Total subject participation will be 29 to 57 days, including the Screening, Clinic, and Follow-up Periods.

Data Monitoring Committee: No

The study will utilize a Dose Escalation Committee to review safety data for Cohort 1 in order to make decisions about dose escalation to Cohort 2. An optional cohort, Cohort 3, may be enrolled based on a review of safety data from Cohorts 1 and 2.

1.2. Schema

Figure 1: Schematic of Study Design

1.3. Schedule of Activities

Table 1: Schedule of Activities

Study Period→		Screening Period	Clinic Period					Follow-up Period
Study Procedure↓	Visit/Day→	Screening Visit Day -36 to Day -8	Check-in Day -1	Dosing Day 1	Days 2 through 6	Day 7	Discharge Day 8 ^{a/} ET	Follow-up Phone Call Day 21 (+3 days)
Informed consent		X						
Eligibility criteria		X	X					
Medical history		X						
Demographics		X						
Body weight & height ^b		X		Pre			X	
Urine drug & alcohol screen		X	X					
Physical examination ^c		X	X	Pre	Pre	Pre	X	
Rectal examination ^d		X	X	Pre	Pre	Pre	X	
Vital signs ^e		X	X	Post: 0.5, 2, 4, and 8h ($\pm 10m$) Pre: 0 ($\leq 25m$)	Days 3 through 6 Pre: 0 ($\leq 25m$)	Post: 0.5, 2, 4, and 8h ($\pm 10m$)		
Orthostatic blood pressure and pulse ^f				Pre: 0 ($\leq 25m$) Post: 1 and 6h ($\pm 20m$)	Day 2 only Pre: 0 ($\leq 25m$)	Pre: 0 ($\leq 25m$) Post: 1 and 6h ($\pm 20m$)	24h post-Day 7 dose ($\pm 20m$)	
TriPLICATE 12-lead ECG ^g		X	X	Pre: 1h ($\pm 30m$) Post: 2h ($\pm 30m$)	Pre: 1h ($\pm 30m$) Post: 2h ($\pm 30m$)	Pre: 1h ($\pm 30m$) Post: 2h ($\pm 30m$)		

Study Period→		Screening Period	Clinic Period					Follow-up Period
Study Procedure↓	Visit/Day→	Screening Visit Day -36 to Day -8	Check-in Day -1	Dosing Day 1	Days 2 through 6	Day 7	Discharge Day 8 ^{a/} ET	Follow-up Phone Call Day 21 (+3 days)
Clinical chemistry, hematology, urinalysis		X	X	Pre: 0 (\leq 15m, \leq 30m for UA) Post: 6h (\pm 30m)	Day 4 only Pre: 0 (\leq 15m, \leq 30m for UA)		X	
ESR and CRP blood draw ^h			X				X	
FSH		X						
HCG ⁱ		X	X					
SARS-CoV-2 testing		X	X					
HIV & hepatitis panel		X						
BBMD training		X						
BBMD dispensed		X	X					
Daily BBMD completion ^j	Day -8 through Day -2	X		X	X	X	X	
BBMD collection and review ^k			X				X	
Concomitant medications		X	X	X	X	X	X	X
AE monitoring		X	X	X	X	X	X	X
Subject confinement to clinic ^l			X	X	X	X	X	
Start of predose fast ^m				Pre: \geq 6h	Pre: \geq 6h	Pre: \geq 6h		
Randomization				X				

Study Period→		Screening Period	Clinic Period					Follow-up Period
Study Procedure↓	Visit/Day→	Screening Visit Day -36 to Day -8	Check-in Day -1	Dosing Day 1	Days 2 through 6	Day 7	Discharge Day 8 ^a / ET	Follow-up Phone Call Day 21 (+3 days)
Study drug administration ⁿ				X	X	X		
PK blood draws ^o				Pre: 0 (≤ 15 m) Post: 0.5 (± 2 m), 1, 2, 4, 6, and 8h (± 20 m)	Pre: 0 (≤ 15 m)	Pre: 0 (≤ 15 m) Post: 0.5 (± 2 m), 1, 2, 4, 6, and 8h (± 20 m)	24h post- Day 7 dose (± 20 m)	
Stool collection ^p			Check-in to Pre: 0h			1 sample collected between Day 7 (postdose) and Day 8 (predischarge)		
Hemoccult testing ^q			X			X		
Follow-up phone call ^r								X

^a Subjects will be discharged on Day 8 unless they have physical examination findings or laboratory abnormalities that are considered by the investigator to be clinically meaningful. In the event that a subject discontinues from the study, an ET Visit will be performed prior to discharge from the CRU. Every effort should be made and documented to ensure that safety procedures scheduled for Discharge are performed at the ET visit.

AE=adverse event; BBMD=bladder and bowel movement diary; CRP=C-reactive protein; CRU=clinical research unit; ECG=electrocardiogram; ESR=erythrocyte sedimentation rate; ET=Early Termination; FSH=follicle-stimulating hormone; HCG: human chorionic gonadotropin; HIV=human immunodeficiency virus; PK=pharmacokinetic; Post=postdose; Pre=predose; SARS-CoV-2=severe acute respiratory syndrome coronavirus 2; UA=urinalysis

^b Height will only be measured at the Screening Visit. On Day 1 (predose) and Discharge (Day 8), subjects will be weighed in the morning upon awakening and before they ingest any water or food.

^c A complete physical examination will be conducted except on Days 1 through 7 when the physical examination will be symptom-directed and conducted prior to study drug administration.

^d Rectal examination at all timepoints should include a digital rectal examination and visual inspection of the perianal area for redness or irritation. If significant redness, rectal pain, fever, bleeding, or mucus is observed, anoscopy may be performed as part of the rectal examination.

^e Vital signs will include oral temperature, blood pressure, and pulse rate. In a semisupine position, blood pressure and pulse will be obtained at the 0.5-hour postdose timepoint on Days 1 and 7 (consistent with the position required following dosing). Blood pressure and pulse at the 2-, 4-, and 8-hour postdose timepoints on Days 1 and 7, as well as predose on Days 3 through 6, should be preceded by at least 5 minutes of rest for the subject in a quiet setting without distractions (eg, television, cell phones). When applicable, vital sign measurements will be obtained before blood draws.

^f For orthostatic blood pressure and pulse measurements, the subject must lie quietly for ≥ 5 minutes before supine/semisupine blood pressure and pulse measurements are taken, then assume standing position for 3 minutes before standing blood pressure and pulse measurements are taken. If a subject has orthostatic symptoms upon standing (eg, palpitation, dizziness), they will be assisted and asked to lie down without waiting the 3 minutes for vital sign assessment. Orthostatic measurements may be taken at other vital signs collection timepoints if clinically indicated, at the discretion of the investigator. When applicable, vital sign measurements will be obtained before blood draws.

^g ECGs should be obtained after the subject has been supine for at least 5 minutes. At each timepoint required, 3 individual ECG tracings should be obtained as closely as possible in succession, but no more than 2 minutes apart. The full set of triplicates should be completed in less than 4 minutes.

^h Elevated inflammatory markers (ESR, CRP), and/or relevant symptoms (eg, rectal pain, hematochezia) may be suggestive of colonic inflammation; subjects with these signs or symptoms should undergo recto-sigmoidoscopy. If this is negative, a colonoscopy may be performed after a discussion between the investigator and the Sponsor.

ⁱ HCG at Screening will be a blood-based test. HCG at Check-in/Day -1 will be a urine-based test.

^j The BM portion of the BBMD will be completed by the subject on an event-driven basis. For subjects with Screening Visits earlier than Day -9, CRU staff will call subjects on Day -9 to remind them to begin recording their BMs in the BBMD the following day, answer any questions, and provide additional BM pages via email, if needed. Bladder information in the BBMD will be collected predose on each dosing day, with a 24-hour recall period at each timepoint.

^k CRU staff will review the subject's Screening Period BBMD at Check-in to confirm that subjects have at least 3 bowel movements during the 7 days prior to Check-in (Days -8 through -2) and no more than 3 bowel movements per day to be eligible for the study; CRU staff will collect the subject's Clinic Period BBMD at Discharge.

^l Subjects will remain at the CRU from Check-in (Day -1) through Discharge (Day 8).

^m Subjects will fast for at least 6 hours prior to dosing on Days 1 through 7 and for at least 1 hour following dosing. During these times, water is permitted.

ⁿ Study drug (IW-3300 or placebo low-volume enema) will be administered rectally once daily, after a fast of at least 6 hours; water is permitted. Subjects will be encouraged to empty their bowels in the morning prior to dosing, if possible. Subjects will be instructed to lie on their left side with their left leg extended and their right leg slightly bent. Study drug will be dispensed in capped syringes with a separately packaged colon tip applicator. The CRU dosing staff will remove the cap from the syringe, attach the colon tip applicator, prime the syringe and applicator to 20 mL, and slowly administer by inserting the contents of the syringe into the rectum. After the full dose has been administered, subjects will lie on their left side for at least 30 minutes to allow the liquid to distribute throughout their intestines, followed by at least 30 additional minutes in the semisupine position. CRU staff will monitor subjects for leakage of the study drug from the rectum during the initial 30 minutes post administration. Subjects should avoid using the bathroom and hold in the enema for as long as possible (at least 1 hour).

^o PK blood draws at 0.5- and 1-hour postdose should be collected while the subject maintains the position noted in the dosing instructions above.

^p At Check-in/Day -1, the subject will bring in a stool sample using the sample collection kit issued by the site. Between Day 7 (postdose) and Day 8 (predischarge), the first stool passed will be collected. If no stool is passed during this time, the subject will be discharged with a stool collection kit and asked to return the sample to the CRU.

^q The predose hemoccult testing may be performed using a stool sample obtained any time from Check-in (Day -1) to predose. If the subject does not produce a stool sample, stool that is present on the Day 1 (predose) digital rectal examination may be used. The Discharge (Day 8) hemoccult testing may be performed using a stool sample obtained any time from postdose on Day 7 to Discharge (Day 8). If the subject does not produce a stool sample, stool that is present on the Discharge (Day 8) digital rectal examination may be used.

^r CRU staff will contact subjects by phone for safety follow-up (at the discretion of the investigator, subjects may be requested to return to the CRU for their follow-up contact).

2. INTRODUCTION

IW-3300 is being developed for the treatment of bladder pain associated with interstitial cystitis/bladder pain syndrome (IC/BPS).

2.1. Study Rationale

This clinical study is the second clinical study designed as a multiple-ascending-dose, safety, and tolerability study with IW-3300. IW-3300 will be administered rectally as a low-volume (20 mL) enema; this route of administration was selected to target the effects of IW-3300 to the afferent nerve fibers in the colonic wall to reduce visceral pain in the pelvic region while minimizing the risk of diarrhea. Dosing for rectal administration will be initiated at 100 µg and will not go higher than 300 µg, which is approximately 80-fold lower than the human-equivalent dose [HED] based on body weight conversion of the lowest no adverse effect level (NOAEL) (24,000 µg) identified in nonclinical toxicology studies.

2.2. Background

IW-3300 is being developed for the treatment of bladder pain associated with IC/BPS. IW-3300 is a novel, 13-amino-acid, guanylate cyclase C (GC-C) agonist peptide. GC-C, the target of IW-3300, is predominantly expressed on the luminal surface of the small and large intestines. Preclinical models provide preliminary evidence which suggests that when GC-C receptors are stimulated, intracellular cyclic guanosine monophosphate (cGMP) is secreted across the basolateral membrane of colonic epithelial cells in the submucosa by multidrug resistance proteins MRP4 and MRP5. This decreases the activity of afferent nerve fibers located in the colonic wall, resulting in reduced visceral pain, which ultimately produces an analgesic effect in other organs of the abdominopelvic region via action mediated through the common afferent pathways.^(1, 2)

Experiments conducted in animals indicate that colonic hypersensitivity induces persistent hypersensitivity of bladder afferent pathways in the absence of bladder pathology.⁽²⁾ Hypersensitivity of bladder afferent pathways resembles the symptoms observed in patients with IC/BPS. Afferent neurons are known to have peripheral endings in both the colon and the bladder, and the axons of colonic and bladder neurons travel through the same splanchnic and pelvic nerves. These nonclinical observations support the concept of cross-organ sensitization and suggest that GC-C agonists such as IW-3300 may be useful clinically for the treatment of bladder pain associated with IC/BPS.

IW-3300 has shown beneficial effects in reducing visceral pain in several animal models, including models of colonic pain and models of extra-intestinal chronic pelvic pain following intracolonic or intrarectal administration. IW-3300 (3 µg/kg/day), administered either intracolonically or orally to female rats, reduced endometriosis-induced mechanical hind paw allodynia. When administered intracolonically (1, 3, or 10 µg/kg/day), IW-3300 reduced endometriosis-induced vulvar pain in a dose-dependent manner. In a rat model of chronic radiation proctopathy induced either by fractionated dose (total dose 48 Gray) or single high dose (25 Gray) of radiation, IW-3300 (3 µg/kg/day) administered intracolonically reversed colorectal and bladder hypersensitivity. IW-3300 (3 µg/kg/day) administered intrarectally reduced vaginal

hypersensitivity in adult female mice previously exposed to neonatal vaginal irritation. In a rat model of early life stress, IW-3300 (3 µg/kg/day) administered intracolonically reduced bladder and mechanical hind paw allodynia in adult male rats.

IW-3300 is a new chemical entity that has similar activity to the naturally occurring peptide hormones guanylin and uroguanylin, which are key regulators of electrolytes. Activation of GC-C expressed on the luminal surface of the intestinal epithelium leads to increased intracellular concentrations of the second messenger cGMP, which triggers a signal transduction cascade leading to the activation of the cystic fibrosis transmembrane conductance regulator (CFTR) through its cGMP-dependent protein kinase G type II (PKGII).⁽³⁻⁵⁾ CFTR activation causes secretion of chloride and bicarbonate into the intestinal lumen, resulting in increased fluid secretion and acceleration of intestinal transit.⁽⁶⁾ These effects occur following oral administration, whereas no significant effects on intestinal transit were observed with direct administration of IW-3300 to the colon in preclinical studies. This was probably due to the high capacity of the large intestine to reabsorb fluid, which can overcome the secretory effects of GC-C when stimulation is limited to the colon. The cellular function and activity of GC-C stimulation is the same regardless of location in the gut; using ligated loops of stomach, small intestine, and colon, GC-C stimulation has been shown to produce increased fluid and cGMP accumulation in all gut tissue.⁽⁷⁾ When stimulation of GC-C is restricted to just the colon, the ability of the colon to reabsorb fluid is greater than the amount of extra fluid produced by activation of GC-C. This is supported by data generated from MD-7246, an investigational delayed-release (DR) formulation of another GC-C agonist, linaclotide, directly into the distal colon in healthy subjects and in patients with irritable bowel syndrome with constipation (IBS-C) or irritable bowel syndrome with diarrhea (IBS-D). In Study MCP-103-105, multiple doses of linaclotide DR (at doses up to 3000 µg) were given once daily to healthy subjects and no diarrhea was reported. In Study MCP-103-205, linaclotide DR doses of 300, 600, or 1200 µg were administered to subjects with IBS-D. The rate of diarrhea TEAEs was low (1.0% to 2.1% in the linaclotide DR dose groups compared with 0% in the placebo group). No severe diarrhea TEAEs were reported.

IW-3300 acts directly on the lumen of the large intestine and has minimal ($\leq 0.2\%$) systemic bioavailability after oral and intrarectal administration in nonclinical species (rodents and monkeys).
[REDACTED]

The safety of IW-3300 has been evaluated in nonclinical repeat dose toxicity, safety pharmacology, and genotoxicity studies and supports evaluation of IW-3300 in humans. IW-3300 was well tolerated when administered intrarectally in rats and monkeys at 20 mg/kg/day for 14 days, with no adverse findings of dehydration or decreases in stool consistency, no local irritation, and no histopathological changes.

IW-3300 is currently under investigation in a Phase 1 single-ascending-dose study in healthy subjects, Study C3300-101. To date, no safety issues have been noted.

Additionally, refer to the [Investigator's Brochure](#) (IB) for a more detailed description of the chemistry and pharmacology of IW-3300.

2.3. Benefit/Risk Assessment

Available data with IW-3300 support a favorable risk-benefit profile. When administered orally, GC-C agonists may cause diarrhea and dehydration. This should be minimized in this study as IW-3300 is being administered intrarectally as a low-volume enema. More detailed information about the known and expected benefits and potential risks of IW-3300 may be found in the [IB](#).

2.3.1. Risk Assessment

Potential Risk of Clinical Significance	Summary of Data/Rationale for Risk	Mitigation Strategy
Study Intervention: IW-3300		
Potential for diarrhea and secondary dehydration	These are class effects of GC-C agonism or effects observed in nonclinical safety pharmacology and toxicology studies of IW-3300.	Intrarectal administration will likely decrease the risk of diarrhea and subsequent dehydration. The study design includes dose escalation to closely monitor subject safety and tolerability at each dose level before dosing with a higher dose; a Dose Escalation Committee will conduct blinded reviews of all the safety parameters of the dosing cohort through Discharge (Day 8) in order to make decisions regarding escalation to the next dose. Orthostatic vital sign measurements will be taken to evaluate the potential for volume depletion. The daily bowel movement (BM) frequency and stool consistency will be monitored in real time to evaluate changes in bowel habits and the potential risk of diarrhea. Stopping rules will also be in place to evaluate continued dosing (Section 7.1.1); dosing within a cohort may be temporarily suspended in the event of a diarrhea or dehydration serious adverse event (SAE); ≥ 1 subject with Grade 3 diarrhea (increase from baseline of >7 stools per day and/or watery stools [Bristol Stool Form Scale {BSFS} score of 7] resulting in a limiting of self-care activities) or dehydration (hospitalization indicated); or ≥ 3 subjects with Grade 2 diarrhea (increase from baseline of 4 to 6 stools per day and/or watery stools [BSFS score of 7] resulting in a limiting of instrumental activities) or dehydration (intravenous fluids indicated).

Potential Risk of Clinical Significance	Summary of Data/Rationale for Risk	Mitigation Strategy
Unknown AEs, laboratory abnormalities, or other safety findings with a novel study drug	This is an early phase study with IW-3300 and, as such, limited clinical data are available.	The study design includes dose escalation to closely monitor subject safety at each dose level before dosing with a higher dose; a Dose Escalation Committee will conduct blinded reviews of all the safety parameters of the dosing cohort through Discharge (Day 8) in order to make decisions regarding escalation to the next dose. Stopping rules are also in place to evaluate continued dosing within a cohort (Section 7.1.1); dosing within a cohort may be temporarily suspended in the event of an SAE considered related to study drug; ≥ 1 subject with a Grade 3 (severe or medically significant) or higher AE considered related to study drug; or ≥ 3 subjects with Grade 2 (moderate) or higher AEs considered related to study drug.
Study drug will be administered rectally.	Rectally administered medications may potentially be associated with AEs such as local trauma/discomfort, irritation, or bleeding.	The study excludes subjects for whom rectal administration would be anticipated to be a safety concern. The low-volume (20 ml) enema used in this study is expected to be a lower risk than higher volume enemas. Nonclinical toxicology studies of IW-3300 have shown no signs of local trauma following intrarectal administration. Study C3300-101, a single-ascending dose clinical study testing IW-3300 doses up to 2500 μ g in healthy subjects is currently ongoing.
Study Procedures		
Venipuncture will be performed during the study.	There is the risk of bleeding, bruising, hematoma formation, and infection at the venipuncture site.	Only appropriately qualified personnel will perform the blood draw. Subjects will be monitored for these risks and managed appropriately.

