6.6. Dose Modification

The decision to proceed to the 300- μ g dose level of IW-3300 (Cohort 2) will be made by the Dose Escalation Committee, based on blinded safety and tolerability data obtained through Discharge on Day 8 in all subjects at the 100- μ g dose level (Cohort 1). The decision to proceed with an optional 3rd cohort will be made by the Dose Escalation Committee based on blinded safety and tolerability data for both Cohorts 1 and 2. The dose will be IW-3300 >100 μ g but <300 μ g.

Dosing at a given dose level may be temporarily suspended for any of the reasons listed in Section [7.1.1](#).

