7. DISCONTINUATION OF STUDY INTERVENTION AND SUBJECT DISCONTINUATION/WITHDRAWAL

7.1. Discontinuation of Study Intervention

It may be necessary for a subject to permanently discontinue study drug. A subject will be discontinued from study drug in the event of:

- A confirmed pregnancy
- A SAE considered by the investigator or Sponsor to be related to study drug

Dosing of study drug for an individual subject may be suspended temporarily as detailed in Section 7.1.1; if the subject is unable to resume dosing, they should follow the instructions for permanent discontinuation below.

If study drug is permanently discontinued, then the subject will have the safety evaluations scheduled for Discharge (Day 8) performed. See the SoA ([Table 1](#)) for data to be collected at the time of discontinuation and follow-up, and for any further evaluations that need to be completed.

If a subject is discontinuing study drug due to an AE, the AE must be followed until it is resolved, stable, or judged by the investigator to be not clinically significant.

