7.1.1. Study Suspension or Termination

Dosing may be temporarily suspended for either dose level if any of the following occur within a cohort:

- ≥ 1 subject with an SAE considered related to study drug
- ≥ 1 subject with an National Cancer Institute Common Terminology Criteria for Adverse Events (NCI-CTCAE) Grade 3 or higher AE considered related to study drug (CTCAE v5.0 will be used; grading criteria are summarized in Appendix 3/ Section [10.3.3.2](#))
- ≥ 3 subjects with CTCAE Grade 2 or higher AEs considered related to study drug

The Dose Escalation Committee should consider the benefit-risk ratio in their determination to suspend dosing temporarily or permanently. If the benefit-risk ratio is considered unacceptable and the effect related to active study drug by the Dose Escalation Committee, dosing at a given dose level will be stopped, and no additional cohorts will be dosed at the same or higher dose level (a lower dose could still be studied).

The sponsor may permanently terminate the study, or a component of the study, at any time. Reasons for termination may include, but are not limited to:

- Death, SAE, or other safety finding considered to be related to IW-3300 that may preclude further dosing

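### Protocol 2.3.1 cites Section 7.1.1 for diarrhea and dehydration suspension triggers that 7.1.1 does not contain, and its stool-count bands skip an increase of exactly 7

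*Protocol*

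**What the plan says.** The risk table in Protocol 2.3.1 opens with diarrhea and secondary dehydration, attributed to the drug class or to nonclinical findings with IW-3300. One of the mitigations is a stopping rule: "Stopping rules will also be in place to evaluate continued dosing (Section 7.1.1); dosing within a cohort may be temporarily suspended". Three triggers follow:

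- a diarrhea or dehydration SAE;
- "≥ 1 subject with Grade 3 diarrhea (increase from baseline of >7 stools per day and/or watery stools" that limit self-care, or dehydration for which hospitalization is indicated;
- "≥ 3 subjects with Grade 2 diarrhea (increase from baseline of 4 to 6 stools per day", or watery stools that limit instrumental activities, or dehydration for which intravenous fluids are indicated.

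None of the three mentions causality. The next row of the table (unknown AEs) cites the same section but does carry a causality condition. Its last trigger reads "≥ 3 subjects with Grade 2 (moderate) or higher AEs considered related to study drug".

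Section 7.1.1 lists a related SAE, a related AE of Grade 3 or higher, and "≥ 3 subjects with CTCAE Grade 2 or higher AEs considered related to study drug". It does not mention diarrhea, dehydration or stool counts. It grades by CTCAE v5.0 and refers to Appendix 3 (10.3.3.2), which gives only general grade descriptors.

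Other sections send the reader to 7.1.1. Protocol 6.6 says "Dosing at a given dose level may be temporarily suspended for any of the reasons listed in Section" 7.1.1. Protocol 7.1 says "Dosing of study drug for an individual subject may be suspended temporarily as detailed in Section 7.1.1". Protocol 4.2 and SAP 4.2 name 7.1.1 as the place where the stopping criteria are set.

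**The concern.** The risk table offers a class-specific rule as protection against the risk that heads it, and gives 7.1.1 as the source. A reader who follows the reference finds a general rule with an added condition. The two give different answers for diarrhea or dehydration that a blinded investigator judges unrelated: the event meets a trigger in 2.3.1 and none in 7.1.1.

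This is the first multiple-dose study of the drug in humans, and the subjects are healthy volunteers. A safety rule described in the risk assessment should be the rule that the site and the Dose Escalation Committee apply. The stool counts that define the diarrhea grades also appear only in 2.3.1, and they leave one whole-number value without a grade.

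**Working it through.** The plan states no figure to reproduce, so the check is a comparison of texts plus a count.

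**Step 1. Set the triggers side by side.**

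| | 2.3.1, diarrhea/dehydration row | 2.3.1, unknown AEs row | 7.1.1 |
|---|---|---|---|
| SAE | Diarrhea or dehydration SAE, any cause | Related SAE | Related SAE |
| Grade 3 | ≥1 subject, any cause | ≥1 subject, Grade 3 or higher, related | ≥1 subject, Grade 3 or higher, related |
| Grade 2 | ≥3 subjects, any cause | ≥3 subjects, Grade 2 or higher, related | ≥3 subjects, Grade 2 or higher, related |
| Triggers that require relatedness | 0 of 3 | 3 of 3 | 3 of 3 |

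The unknown AEs row reproduces 7.1.1. The diarrhea row does not, although it cites the same section.

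**Step 2. Test whether either rule contains the other.** These are constructed cases within one cohort of 9.

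- Three subjects have Grade 2 diarrhea; two are judged related and one unrelated. The 2.3.1 diarrhea count is 3, so its trigger is met. The 7.1.1 count is 2, so its trigger is not met.
- One subject has a dehydration SAE judged unrelated. The 2.3.1 trigger is met; the 7.1.1 SAE trigger is not.
- Three subjects each have one related Grade 2 event: diarrhea, headache and rectal pain. The 2.3.1 diarrhea count is 1, so its trigger is not met. The 7.1.1 count is 3, so its trigger is met.

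Neither rule contains the other. The 2.3.1 row is wider on causality, and 7.1.1 is wider because it pools all AE types. That 7.1.1 says Grade 2 or higher, where the diarrhea row says Grade 2, adds little: one Grade 3 subject already meets the 2.3.1 row.

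**Step 3. See which text would be applied.** Protocol 4.2, 6.6 and 7.1 and SAP 4.2 refer to 7.1.1 for suspension or stopping, and none of them refers to 2.3.1. Section 7.1 likewise ties SAE-based discontinuation of a subject to causality: "A SAE considered by the investigator or Sponsor to be related to study drug". In practice 7.1.1 would be followed.

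**Step 4. Check the stool-count bands in 2.3.1 on whole numbers.**

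| Increase from baseline (stools per day) | Grade by count |
|---|---|
| 4, 5, 6 | 2 |
| 7 | none |
| 8 or more | 3 |

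Only the count criterion has the gap. A subject at +7 could still be graded through the watery-stool limb or through CTCAE v5.0, which 7.1.1 names. The documents do not reproduce the CTCAE stool counts, so they do not settle which band should take 7.

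**The case against.** The strongest reply is that 2.3.1 is a summary table that defers to 7.1.1, and that the relatedness phrase was probably just left out of one row. The parallel row and the discontinuation rule in 7.1 both require relatedness, which fits that view. A reader might infer that the site could not tell which rule governs. The documents do not support that, because the cross-references all lead to 7.1.1. What stands is that the governing text is not the one offered as mitigation.

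A reader might also infer that unrelated diarrhea or dehydration is left without any response. That is not supported either. Section 8 requires immediate safety concerns to be discussed with the sponsor, with no causality condition. Section 7.2 lets the investigator withdraw a subject for safety at any time. Section 7.1.1 lets the sponsor terminate the study or part of it at any time, for reasons that are not confined to related events. Section 8.3.1 sends every SAE to the sponsor within 24 hours. Suspension is optional in both trigger lists, so a missing trigger stops no one from acting. These routes limit the consequence, but general discretion is not a pre-specified trigger.

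Finally, few events may be in dispute. Diarrhea in a confined subject dosed daily by enema would probably be called unrelated mainly when another cause is evident. That is plausible, but Section 10.3.3.3 asks for positive grounds for a causal link, not merely that a link cannot be excluded. A blinded investigator could therefore judge such an event unrelated in good faith.

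**Conclusion.** The inconsistency is real and should be corrected. Relatedness is required in 0 of 3 triggers in the 2.3.1 diarrhea row and in 3 of 3 in 7.1.1, and one count value (+7) falls in neither band. This rests on two readings: that silence about causality in 2.3.1 means no causality condition, which the contrast with the next row supports; and that 7.1.1 is the rule applied, which the cross-references support.

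The effect is confined to formal within-cohort triggers for events judged unrelated. Related Grade 2 or 3 events and related SAEs already count under 7.1.1. The review before escalation covers all Cohort 1 safety data through Day 8 whatever the causality. No endpoint or analysis changes.

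A reader might try to size the problem from the 1.0% to 2.1% diarrhea rates in Protocol 2.2. Those rates do not support a frequency claim in either direction. They come from a delayed-release formulation of another agonist in patients with IBS-D, they are observed rates rather than upper limits, they do not separate related from unrelated events, and they do not cover dehydration. Sizing the disagreement would need the rate of qualifying events with IW-3300 enema and the share judged unrelated, and the documents give neither. The case for the change is consistency of a safety rule, not expected frequency.

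**What to change.** Make 2.3.1 and 7.1.1 state one rule.

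- **Preferred:** add a diarrhea and dehydration block to 7.1.1 that applies regardless of causality, with the three triggers and the definitions now found only in 2.3.1. This is the more protective reading for a known class effect. Keep suspension optional and temporary, and keep the committee's judgment that the effect is related to active drug before a permanent stop.
- **Alternative:** if the sponsor meant relatedness to apply throughout, add to the diarrhea row of 2.3.1 the relatedness qualifier that the next row already carries.

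In either case, make the stool-count bands contiguous. Writing the Grade 3 band as ≥7 is the cautious closure. Extending Grade 2 to 4 to 7 would also close the gap, so the sponsor should check the choice against CTCAE v5.0.

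The cost is one added block in 7.1.1 or one phrase in 2.3.1, plus one symbol. No procedures or subjects are added, because 2.3.1 already provides for real-time monitoring of bowel movement frequency and stool consistency. The downside of the preferred route is an occasional extra committee review.
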